I, the undersigned, have reviewed this protocol, including the appendices and I will conduct the study as described in compliance with this protocol, GCP and relevant International Council on Harmonisation (ICH) guidelines.

Once the protocol has been approved by the Human Research Ethics Committee (HREC), I will not modify this protocol without obtaining prior agreement and approval from CSIRO/A*STAR Principal Investigator (PI) and the HREC. I will submit the protocol modification and/or any Informed Consent Form (ICF) modifications to the CSIRO/A*STAR PI and HREC and approval will be obtained before any modifications are implemented.

I understand that all the information obtained during the conduct of the study with regard to the participants' state of health will be regarded as confidential. No participants' names will be disclosed. All Participants will be identified by assigned numbers on all case report forms (CRF), laboratory samples or source documents. Clinical information may be reviewed by regulatory agencies. Agreement must be obtained from the participant before disclosure of participant information to a third party.

INVESTIGATOR SIGNATURE:

PRINTED NAME: [name]

COMPANY/POSITION: CSIRO

SIGNATURE: 

INVESTIGATOR SIGNATURE:

PRINTED NAME: [name]

COMPANY/POSITION: A*STAR

SIGNATURE: 

Study Synopsis

Protocol Title:	Bioavailability of omega-3 long-chain polyunsaturated fatty acids (LCPUFA) from foods enriched with vegetable-encapsulated omega-3 oils
Aim:	To compare the bioavailability of omega-3 LCPUFA from two test food products containing vegetable-encapsulated omega-3 algal oil against a control test product (algal oil gel capsules) across two ethnicities (Australian European vs. Chinese Singaporean).
Study Design:	Multi-centre, randomised, controlled, acute, 3-way cross-over study design. Participants will consume in random order, at least 1-week apart, three test products after an overnight fast. Blood samples will be collected at 0, 2, 4, 6, 8 and 24 hours after consuming the products. Plasma fatty acid concentrations ($\mu\text{g/mL}$) will be analysed by gas chromatography and bioavailability of omega-3 LCPUFA determined by calculating the incremental area under the curve ($i\text{AUC}_{0-24\text{h}}$), time to maximal value (T_{max}) and maximal value (C_{max}).
Study sites:	CSIRO Nutrition and Health Research Clinic, Adelaide A*STAR Clinical Nutrition Research Centre, Singapore
Number of Participants:	N=24 (n=12 in Australia and n=12 in Singapore) Accounts for 20% attrition.
Inclusion/Exclusion Criteria:	
INCLUSION CRITERIA:
 
 1. Healthy men, 21-50-year old 2. BMI 18-27.5 kg/m^2 3. Consuming <2 meals of fatty fish/week and no fish oil supplements 4. Ethnicity 
 ○ If Australian site: Australian European 
OR
 
 ○ If Singapore site: Chinese Singaporean 
EXCLUSION CRITERIA:
 
 1. Self-reported history of chronic disease - cancer, type 2 diabetes, cardiovascular disease, liver disease or any condition that may, in the opinion of the principle investigator, influence the study outcomes. 2. Self-reported history of gastrointestinal disease, pancreatic insufficiency, conditions resulting in fat malabsorption - chronic pancreatitis, cystic fibrosis, coeliac disease, Crohns disease, gastric bypass surgery, small bowel resection, abnormal thyroid function 3. Bleeding disorders, currently taking anticoagulants or has received anticoagulants within 28 days of Day 1 of the trial, with the exception of low dose aspirin up to 150 mg daily* 4. Any medical procedures deemed by the principal investigator to affect study outcomes

	
 5. Known food allergies, hypersensitivity, dietary avoidance or intolerance to the study foods 6. Taking medications/supplements known to influence lipid metabolism and gastric emptying 7. On any weight-loss program 8. History of smoking during the 6 months prior to the study 9. Persons considered by the investigator to be unwilling, unlikely or unable to comprehend or comply with the study protocol. 10. Self-reported history of drug abuse or alcoholism 11. Participation in another research study within 30 days preceding the start of this study
Treatment:	
Standardised breakfast plus:
 
Test food 1: Semi-solid food – Soup (commercially available packet-soup) containing cauliflower encapsulated HiDHA® algal oil providing 400 mg DHA
 
Test food 2: Solid food – Extruded snack (savory snack) containing cauliflower encapsulated HiDHA® algal oil providing 400 mg DHA
 
Control: 2x Algal oil gel capsules containing HiDHA® algal oil providing 400 mg DHA

Study Duration:	~1 month (3 test products at least 1-week apart)
Study Population:	Healthy men
Primary Outcome:	Plasma DHA and total omega-3 LCPUFA iAUC _{0-24h}

List of Abbreviations

Abbreviation	Description
AE	Adverse Event
AUC	Area under the curve
BMI	Body mass index
CHD	Coronary heart disease
CRF	Case report form
CVD	Cardiovascular disease
DHA	Docosahexaenoic acid
EPA	Eicosapentaenoic acid
EW	Early Withdraw
FRAT	Food risk assessment team
HREC	Human Research Ethics Committee
ICF	Informed Consent Form
ICH-GCP	International Council for Harmonisation Good Clinical Practice
LCPUFA	Long-chain polyunsaturated fatty acids
NCD	Non-communicable disease
SAE	Serious adverse events

1. Introduction

Non-communicable chronic diseases (NCD) in both Australia and Singapore account for significant proportions of deaths, disease burden and hospitalizations, with poor quality diet as the major contributor to the NCD burden (1, 2). Marine derived omega-3 long-chain polyunsaturated fatty acids (LCPUFA) (particularly eicosapentaenoic acid (EPA) and docosahexaenoic acid (DHA) are associated with numerous health benefits throughout the life cycle. Omega-3 Index (O3I) (EPA+DHA as % of red blood cell fatty acids – a biomarker of EPA+DHA status (3)) levels of 8% vs. 4% were related to a 30% reduced risk of fatal coronary heart disease (CHD) (4). More recently O3I levels at 8% have also been linked to increased longevity, reduced all-cause mortality, improved depressive symptoms, improved arthritis symptoms (5) and improved cognitive function (6). Despite the well-established health benefits of omega-3 LCPUFA, intakes in Western and most Asian diets are below recommendations (7, 8), and low levels of consumption have been associated with an increased risk of cardiovascular mortality in a Chinese population (7). Consumption of ~2-3 serves/week of fish, including oily fish, is recommended to achieve ~250 – 500 mg/day of combined EPA+DHA, and up to 1g/day for those with CHD (9-11). Achieving these intakes through dietary means is challenging, particularly for individuals who do not consume fish or seafood (major dietary sources of omega-3 LCPUFA) (5). Vegans and vegetarians are particularly at risk. Several studies have shown that vegan diets are devoid of DHA and vegetarian diets that include dairy food and eggs only provide about 0.02 g DHA/day. These low intakes were accompanied by substantially lower levels of DHA in plasma, serum, red blood cells (RBC) and plasma phospholipids (PL) in vegans and vegetarians compared to omnivores (12). Furthermore, a high degree of inter-individual variability exists in how omega-3 intake affects O3I levels (5). Dose, baseline omega-3 status and chemical form of supplements have been shown to affect O3I levels in response to intake (13). Other factors such as characteristics of food products and individuals' ethnicity have potential to impact O3I but have not been formally investigated previously. A better understanding of factors affecting response to increased omega-3 LCPUFA intakes will assist in the development of personalized approaches to assist consumers in achieving omega-3 status that is optimal for health. Furthermore, despite convincing evidence that diets rich in vegetables are associated with reduced risk of all-cause mortality and particularly cardiovascular mortality (14), populations globally fail to meet recommended intakes (15). Hence, strategies empowering consumers to achieve omega-3 LCPUFA and vegetable intake targets have potential to significantly impact health outcomes.

Some of the challenges in the production of foods fortified with omega-3 fatty acids include their undesirable odour and taste and their susceptibility to oxidative degradation (16). CSIRO has developed a novel vegetable-based encapsulation system for delivery of omega-3 LCPUFA which provides superior protection against oxidation of omega-3 fatty acids compared to other commercially available microencapsulation techniques (17), while at the same time delivering the nutritional benefits of vegetable consumption. Vegetable encapsulated omega-3 fortified food has the potential to deliver daily recommended dosage of omega-3 fatty acids (~250-500 mg/serve) in addition to a serving of vegetables. In addition, if a vegetarian omega-3 LCPUFA oil is used (e.g. algal oil), these products will also be suitable for vegans and vegetarians. One of the challenges in incorporating vegetable encapsulated omega-3 LCPUFA into fortified foods is the potential effect of the vegetable carrier matrix (e.g. fibre and other bioactives) on release and bioavailability of omega-3 LCPUFA *in vivo*. Furthermore, there is a possibility of inter-ethnic differences in omega-3 bioavailability. Heritability and anthropometric phenotypes, previously associated with omega-3 status (18), differ between Asian and Caucasian populations. The current project aims to address these challenges and to use the data generated as the basis for development of personalised formulations tailored to improve omega-3 status and vegetable intake and consequently health outcomes of consumers in Australia and Singapore.

2. Aim, Objectives and Hypotheses

Aim:

To evaluate the bioavailability of omega-3 LCPUFA from foods enriched with vegetable-encapsulated omega-3 oils across two ethnicities.

Objective/s:

- To compare the bioavailability of omega-3 LCPUFA from two test food products containing vegetable-encapsulated omega-3 algal oil against a control test product (algal oil gel capsules).
- To evaluate whether ethnic background (Australian European vs. Chinese Singaporean) affects the bioavailability of omega-3 LCPUFA when consuming vegetable-encapsulated omega-3 products relative to a control test product.

Hypotheses:

H0: Delivery of omega-3 LCPUFA with vegetables as carriers does not impact bioavailability.

H0: Bioavailability of omega-3 LCPUFA is not influenced by inter-ethnic differences.

Outcomes:

- Primary outcome: Incremental area under the plasma DHA and total omega-3 LCPUFA concentration ($\mu\text{g/mL}$) curves ($i\text{AUC}_{0-24\text{h}}$)
- Secondary outcomes: Time to maximal value (T_{max}) and maximal value (C_{max}) on the plasma DHA and total omega-3 LCPUFA concentration ($\mu\text{g/mL}$) curves.

3. Study Population

N=24 (N=12 in Australia; N=12 in Singapore) healthy men. Men are chosen as study population to ensure a homogenous population.

4.1 Inclusion and Exclusion criteria

Inclusion Criteria

1. Healthy men*, 21-50-year old**
2. BMI 18-27.5 kg/m^2
3. Consume <2 meals of fatty fish/week
4. Not Consume fish oil supplements over the past 3 months
5. Ethnicity
 - a. If Australian site: Australian EuropeanOR
 - b. If Singapore site: Chinese Singaporean

* Only males will be recruited to ensure a metabolically homogenous sample

** The lower-end age criteria has been increased from the typical 18 to 21 to provide consistency with Singaporean recruitment criteria (Participants under the age of 21 require guardian approval in Singapore).

Exclusion Criteria

1. History of chronic disease - cancer, type 2 diabetes, cardiovascular disease, liver disease or any condition that may, in the opinion of the principle investigator, influence the study outcomes*
2. History of gastrointestinal disease, pancreatic insufficiency, conditions resulting in fat malabsorption - chronic pancreatitis, cystic fibrosis, coeliac disease, Crohns disease, gastric bypass surgery, small bowel resection, abnormal thyroid function*
3. Bleeding disorders, currently taking anticoagulants or has received anticoagulants within 28 days of Day 1 of the trial, with the exception of low dose aspirin up to 150 mg daily*
4. Any medical procedures deemed by the principal investigator to affect study outcomes
5. Known food allergies, hypersensitivity, dietary avoidance or intolerance to the study foods
6. Taking medications/supplements known to influence lipid metabolism and gastric emptying
7. On any weight-loss program
8. History of smoking during the 6 months prior to the study*
9. Persons considered by the investigator to be unwilling, unlikely or unable to comprehend or comply with the study protocol
10. History of drug abuse or alcoholism*
11. Participation in another research study within 30 days preceding the start of this study

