***Self-reported, no clinical testing will be performed.**

4. Study Design and procedures

A multi-centre, randomised, controlled, acute, 3-way cross-over single-blind study design will be used. The trial will be performed at CSIRO's Nutrition and Health Research Clinic, Adelaide (n=12) and A*STAR's Clinical Nutrition Research Centre in Singapore (n=12).

Participants will attend a screening visit to confirm their eligibility for inclusion into the trial (Figure 1). If eligible, participants will remain at the clinic where they will be enrolled into the study and participate in the first intervention on that day (Screening will be conducted at V1). After enrolment participants will attend the research clinic for test procedures on 3 occasions at least 1-week apart during which they will consume one of three test products at each occasion in random order. Participants will attend the clinic on 6 occasions in total (to include returning for 24hr blood sample) – visits 2, 4 and 6 (Figure 1). A 1-week washout period is sufficient for plasma sample to return to baseline (19). Participants will be randomly assigned by computer sequence generation (<http://www.randomisation.com>) to one of three treatment orders (Figure 1). The random allocation sequence will be generated by a staff member not involved with entering participants into the trial to ensure allocation concealment.

[figure not shown]

Figure 1. Study design

Participants will visit the research clinic on six occasions (Figure 1).

- Occasion 1: Screening + 1st intervention (randomised) involving in-clinic assessments (~9 hours).
- Occasion 2: Participants will return to the clinic for a short visit (30 minutes) where a 24-hour blood sample will be collected (Figure 2).
- Occasion 3: (1 week following Occasion 1) 2nd intervention (randomised) involving in-clinic assessments (~8.5 hours).
- Occasion 4: Participants return to the clinic for a short visit (30 minutes) where a 24-hour blood sample will be collected.
- Occasion 5: (1 week following Occasion 3) 3rd intervention (randomised) involving in-clinic assessments (~8.5 hours).
- Occasion 6: Participants return to the clinic for a short visit (30 minutes) where a 24-hour blood sample will be collected.

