Screening occasion: Participants will be pre-screened using a screening questionnaire and those determined to be potentially eligible will be invited to attend an in-clinic screening visit. After they have given signed informed consent (see details below) their eligibility will be confirmed by reviewing their medical history, demographic information and fatty fish intake obtained from the screening questionnaire, measuring height and weight and calculating BMI, and measuring vital signs (blood pressure and temperature). Eligible participants will be enrolled into the study and remain at the clinic for further 8.5 hours and complete their first intervention

Intervention occasions (Figure 2): Participants will arrive at the research clinic after an overnight fast (>10h)). Weight, percentage body fat mass and vital signs (blood pressure and temperature) will be measured, an intravenous cannula will be inserted into the participants arm for a duration of 8 hours during which the participant will remain at the research clinic.

A fasting blood sample (4 mL) will be collected after which participants will consume a standardised breakfast with their test product (see section 5 for more detail) within 15 minutes. Subsequent blood samples will be collected after 2, 4, 6 and 8 hours. The cannula will be removed, and participants will leave the research clinic. Participants will return to the research clinic the next morning after an overnight fast for collection of the 24-hour sample. The period of 24 hours was chosen as it represents an intake interval of daily intake of omega-3 supplements (19). Throughout the 9-hour day at the clinic participants will have access to low-fat snacks and a lunch meal devoid of omega-3 LCPUFA that they can consume *ad libitum* (see section 5 for more detail). Participants will leave the clinic with a take-home low-fat dinner meal.

Apart from the study specific test products, participants will be requested to maintain their habitual lifestyle patterns throughout the duration of the study and to avoid fatty fish and omega-3 LCPUFA containing supplements. Participants will be provided with a checklist to record any non-compliance or accidental consumption of these foods and return the checklist at their subsequent visit.

Staff responsible for sample and statistical analysis will be blinded to which treatment was consumed when, but participants and staff administering treatments will not be blinded.

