The Principal investigator or designee may withdraw a participant from the study at any time. In this event, the clinic will ensure the reasons have been clearly explained to the individual. Adverse event and concomitant medications will be reviewed at the time of withdrawal. A two-week follow-up will be performed for any unresolved AE at the time of withdrawal.

5. Test meals

Test meals:

1. Semi-solid food – 200 g serve Soup (commercially available packet-soup) containing cauliflower encapsulated HiDHA[®] algal oil providing 400 mg DHA + standardised breakfast
2. Solid food – 50 g serve extruded snack (savory snack) containing cauliflower encapsulated HiDHA[®] algal oil providing 400 mg DHA + standardised breakfast
3. Control: 2 x algal oil gel capsule containing HiDHA[®] algal oil providing 400 mg DHA + standardised breakfast

HiDHA[®] algal oil will be supplied by NuMega Ingredients Pty Ltd.

The standardised breakfast will consist of a small carton of Milo (Nestle: 200 ml), an apple (200 g), one muesli bar (Uncle Toby's: 24 g) (total energy = ~1600 kJ) and the test products/control.

Throughout the 8-hour day at the clinic participants will have access to low-fat snacks and a lunch meal devoid of omega-3 LCPUFA that they can consume *ad libitum*. Low-fat is defined as ≤ 3 g fat/100 g solid food or ≤ 1.5 g fat/100 ml for liquid food (20, 21). Snacks may include rice crackers, fruit, low-fat dairy products (yoghurt, chocolate milk), fruit juice, water, etc. Lunch and dinner meals will be low-fat frozen meals selected from the Lean Cuisine Steam range available in both Australia and Singapore (<https://www.vescofoods.com.au/brands/lean-cuisine>). Breakfast (selection of cereal) will be provided to participants after collection of the 24-hour sample.

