The test products will be manufactured in facilities certified for production of food for human consumption in accordance with an approved HACCP (Hazard Analysis Critical Control Point) plan. Only food grade ingredients will be used in the production process. All the equipment that will be used in the production process will be sanitised, swabbed for microbial contamination and recleaned until it becomes suitable for food contact. All the processing steps, from the purchase of the ingredients to the processing and handling conditions at each processing stage will be recorded in a process log sheet. The microbial and physicochemical quality of the final products will be tested in accordance with the approved HACCP plan. The products will be released as fit for human consumption after the Food Risk Assessment Team (FRAT) team examined the process log sheet and the results of the microbial and physicochemical analyses.

7. Assessments

Medical history and demographic information:

Medical and surgical history, medication and supplement use and demographic information will be obtained by questionnaire and interview of participants. This information will be used to screen participants.

Assessment of fatty fish intake:

In order to assess participant's eligibility to inclusion criteria 3 - "Consuming <2 meals of fatty fish/week over the past 3 months", potential participants will be asked to record the frequency and type of fish they habitually consume. E.g. "How often do you consume fish?" Frequency options will include <1x/month, 1-3x/month, 1x/week, 2x/week, 3-4x/week, 1x/day, >1x/day. "What type of fish do you usually consume". The categories of fish according to fatty fish / medium- or low-fat fish sources are summarised in the Appendix and will be used to determine participant's eligibility accordingly.

Anthropometric measurements:

Height and weight will be measured at the screening visit and BMI calculated using the formula: weight (kg)/height (m)². Weight will also be collected at each clinic visit. Height will be measured using a stadiometer and body weight will be measured using calibrated electronic digital scales.

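### The supplement entry criterion names only fish oil while the on-study rule covers every omega-3 LCPUFA supplement, so a user of algal DHA, the oil under test, meets inclusion criterion 4

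*Combined protocol and SAP*

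**What the plan says.** Section 4.1, inclusion criterion 4, requires: "Not Consume fish oil supplements over the past 3 months". The Synopsis merges this with the fish criterion as "Consuming <2 meals of fatty fish/week and no fish oil supplements", with no time window. During the study, section 4 (Intervention occasions) asks participants "to avoid fatty fish and omega-3 LCPUFA containing supplements".

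Two other provisions bear on supplements. Exclusion criterion 6 bars men "Taking medications/supplements known to influence lipid metabolism and gastric emptying". Section 7 says: "Medical and surgical history, medication and supplement use and demographic information will be obtained by questionnaire and interview of participants", and that this information is used for screening.

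On timing, section 4 states "Screening will be conducted at V1", and eligible men stay for their first intervention that day. On the product, section 5 describes the control as an "algal oil gel capsule containing HiDHA" oil, two capsules giving 400 mg DHA. Both test foods carry the same oil and the same amount of DHA.

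Section 8 calculates the 0–24 h iAUC by the trapezoidal rule with correction to baseline. It lists fixed effects for treatment, time and ethnicity, two interactions and a random participant intercept. It lists no period or sequence effect. It sizes the trial at 10 men per site for a 10% difference in AUC and recruits 12.

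**The concern.** The entry rule and the on-study rule should cover the same products. Here the entry rule is narrower, and the gap includes the class of product being tested. The introduction itself presents algal oil as the source suitable for vegans and vegetarians, so users of non-fish omega-3 products are within the protocol's own field of view.

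The documents describe no run-in. A man who met criterion 4 while using algal DHA would have to stop at some point around his first visit. If his plasma DHA is still falling on a test day, part of the rise after dosing is hidden and that day's iAUC is too low.

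Separately, the two statements of the criterion disagree on the window. A man who stopped fish oil two weeks ago satisfies the Synopsis and fails section 4.1.

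**Working it through.** **1. Which rule reaches whom**

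| Man at screening | Synopsis | Section 4.1, inclusion 4 | Exclusion 6 | On-study rule |
|---|---|---|---|---|
| Daily algal DHA user | passes | passes | site's judgement | must stop |
| Stopped algal DHA a few days earlier | passes | passes | not reached (present tense, no look-back) | already complies |
| Stopped fish oil two weeks earlier | passes | fails | not reached | already complies |

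Exclusion 6 does not mention omega-3 and joins two effects with *and*, so sites may read it differently. Section 7 collects supplement use but does not say which answer excludes. The items that section 4 lists for confirming eligibility include medical history, demographics and fatty fish intake; supplement use is not named there.

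**2. What baseline correction leaves behind**

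Each test day has its own fasting sample, so a different starting level at each visit is subtracted out. A fall during the 24 hours is not. For a linear background fall of d µg/mL over 24 h, net iAUC loses 24 × d / 2 = 12d µg·h/mL.

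**3. How the loss could spread over periods**

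The documents give no decay rate after regular use, so the half-life h is assumed over a range. Let E (µg/mL) be the excess over the man's unsupplemented level at the first fasting sample; E is also unknown. On a test day starting D days later (D = 0, 7, 14), the background at t hours is E × 2^(−(D + t/24)/h). Subtract its value at t = 0 and apply the trapezoidal rule at 0, 2, 4, 6, 8 and 24 h:

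| h (days, assumed) | 24 h fall, period 1 | iAUC shift, period 1 | period 2 | period 3 | period 1 minus period 2 |
|---|---|---|---|---|---|
| 2 | 29% of E | −3.66E | −0.32E | −0.03E | −3.34E |
| 3 | 21% of E | −2.54E | −0.50E | −0.10E | −2.04E |
| 7 | 9% of E | −1.14E | −0.57E | −0.29E | −0.57E |
| 14 | 5% of E | −0.58E | −0.41E | −0.29E | −0.17E |

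The shift is downward throughout and largest in period 1. The last column is what enters that man's treatment comparison between those two periods. With a long half-life most of the shift cancels.

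**4. Scale at group level**

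The plan's own numbers are 10 analysed and 12 recruited per site: 10 × 1.2 = 12 (dividing instead gives 10 / 0.8 = 12.5). The point does not depend on which is used. If one man's value shifts by 10%:

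- site mean: 10% / 10 = 1.0%, or 10% / 12 = 0.8%;
- both sites together: 10% / 20 = 0.5%, or 10% / 24 = 0.4%.

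For comparison, section 8 gives no SD. A two-sided paired t-test at 0.05 with n = 10 reaches 80% power for a 10% difference only if the SD of the paired difference is about 10% (power 80.3% at that SD). The standard error is then 10 / √10 = 3.2 percentage points, so a 1-point shift is about a third of one standard error.

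**The case against.** The strongest reply is that fish oil is not the only supplement restriction. Exclusion 6 is in the present tense and can reach a current daily user if the site regards algal DHA as acting on lipid metabolism, and supplement use is asked about at screening. That stands: a reader might infer from criterion 4 that eligibility bars fish oil and nothing else, and the documents do not support that. What remains is that the decision is left to each site and that a recent user is not reached at all.

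Several stronger readings are tempting and also unsupported:

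- *That such a man is certain to be tested on a falling baseline.* This needs him to enrol, and the documents give neither a decay rate nor a frequency of algal or krill oil use. Candidates are pre-screened before the first visit, and the documents do not say when they are first told to avoid supplements.
- *That a fall of about 2 µg/mL would match the 10% difference the trial is sized for.* With an assumed mean rise of 10 µg/mL, iAUC is 240 µg·h/mL, 10% of it is 24, and 24 / 12 = 2. The fall is solved backwards from the target, and it sets one man's shift in one period against a group difference.
- *That the introduction shows baseline status changes this outcome.* Its statement concerns the Omega-3 Index, a red-cell percentage, not 24 h plasma iAUC.
- *That the crossover breaks down.* Visit-specific baselines remove level differences and order is randomised. If the three orders place each treatment equally often in each period (Figure 1 is not shown), the drift mainly adds noise rather than treatment bias.

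The missing window in the Synopsis can fairly be called editorial. It still gives a different eligibility answer for the same man.

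**Conclusion.** The mismatch is plain in the text: fish oil at entry, all omega-3 LCPUFA supplements on study, and a look-back in only one of the two entry statements. A regular or recent algal DHA user meets inclusion 4, exclusion 6 is not a dependable backstop, and same-day screening and dosing leaves no interval for his plasma to settle.

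The consequence is conditional and probably small. It requires such a man to be enrolled and still falling, its size in µg·h/mL cannot be derived from the documents, and the half-lives above are assumptions. A 10% shift in one man amounts to 0.8–1.0% of a site mean and 0.4–0.5% over both sites. No listed model term would absorb a period effect. The case for acting is that the stated rule admits participants the on-study rule shows are unwanted, and that correcting it is nearly free.

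**What to change.** Reword criterion 4 in section 4.1 and the matching Synopsis line along these lines: *no use of supplements containing omega-3 LCPUFA (fish, algal, krill or any other source of EPA or DHA) over the past 3 months*. Entry and on-study rules would then cover the same products, and both entry statements would carry the same window. Three months is the window already in section 4.1; the investigators should confirm that it suits the wider product list.

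The cost is a few words in two places and one explicit item on the screening questionnaire, which already records supplement use. The downside is that a few algal or krill oil users become ineligible. Sample size and analysis are unchanged.
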